5 STUDY LIMITATIONS/STRENGTHS

5.1 Limitations Linked to Data Sources

As the study is based on fully anonymized real life, electronic medical records data, there are limitations inherent to the impossibility to link data from different databases and to get additional information from the physicians.

Data are collected by GPs: Even if some patients with type 2 diabetes mellitus may be treated exclusively by specialists, most of them will be treated by their GP at least for the treatment maintenance period. This study will not capture any use of dapagliflozin that is prescribed by specialists in Europe.

Data are collected in routine care: Cegedim's LPDs collect real life clinical practice information from the actual medical patients' records. A study specific CRF will not be used to collect supplemental information not entered in the medical records as part of the patient's routine clinical care. Also, as a non-interventional study, this protocol does not mandate any study specific visits or procedures.

Potential for missing data: No individual patient identifiers will be available. It is therefore impossible to query the physicians providing the data for any missing information.

¹ Dapagliflozin uptake was estimated from AZ forecasting models.

Data not recorded correctly in the databases: Recording of the indication of each prescribed treatment is mandatory in the Cegedim Software but the GP is free to enter any diagnosis and can for instance enter the reason of visit (*e.g.* flu) as indication for all treatments prescribed at the visit, and an oral antidiabetic drug may thus be recorded with an indication 'flu'.

Incomplete data: Clinical laboratory results are entered by the GPs whenever they deem these results relevant. The patient's renal function is therefore uncertain in the absence of recent creatinine. Similarly, weight may not be recorded by the physician at each consultation, which may impact the calculation of creatinine clearance calculation.

Absence of systematic recording of referrals to specialists: Except for the UK database, there is no systematic recording of referrals. If dapagliflozin is a secondary care initiation, this will not be recorded, leading to misclassification bias for newly initiated patients.

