Page: 1

Protocol Number: MB102134

Date: 13-Nov-2013

Observational Study Protocol MB102134

OBSERVATIONAL SINGLE-COHORT DATA BASE STUDY OF DAPAGLIFLOZIN UTILISATION IN EUROPE

This document is the confidential and proprietary information of Bristol-Myers Squibb Company, its global affiliates (BMS) and AstraZeneca (AZ). By reviewing this document, you agree to keep it confidential and to use and disclose it solely for the purpose of assessing whether your organization will participate in and/or the performance of the proposed BMS/AZ-sponsored study. Any permitted disclosures will be made only on a confidential "need to know" basis within your organization or to your independent ethics committee(s). Any other use, copying, disclosure or dissemination of this information is strictly prohibited unless expressly authorized in writing by BMS/AZ. Any supplemental information (e.g., amendments) that may be added to this document is also confidential and proprietary to BMS/AZ and must be kept in confidence in the same manner as the contents of this document. Any person who receives this document without due authorization from BMS/AZ is requested to return it to BMS/AZ or promptly destroy it. All other rights reserved.

SYNOPSIS

Observational Study Protocol MB102134

Protocol Title: Observational Single-Cohort Data Base Study of Dapagliflozin Utilisation in Europe

Department: Bristol-Myers Squibb Epidemiology and AstraZeneca Global Epidemiology

Objective(s): *Primary objective:* To describe the characteristics of European patients newly prescribed dapagliflozin by age, sex, dapagliflozin dose, country, selected co-morbidities, and selected concomitant medications.

The proposed drug utilization study will specifically describe dapagliflozin use in:

- patients > 75 years-old,
- combination use with loop diuretics or pioglitazone,
- patients with a known history of moderate or severe renal impairment and in kidney failure,
- patients lacking a diagnostic code indicating type 2 diabetes.

Study Design: This is an observational single-cohort data base study with descriptive data analyses among patients receiving dapagliflozin within electronic medical records in Europe. The study will describe the utilization pattern of dapagliflozin during the first 3.5 years after marketing authorization and launch in Europe specifically in Belgium, France, Germany, Italy, Spain and United Kingdom.

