Study Population: All patients identified in the database(s) who newly received at least one dapagliflozin prescription during the study period. Dapagliflozin use will be representative of the uptake of dapagliflozin in the respective countries.

Data Collection Methods: Cegedim Strategic Data (CSD) Longitudinal Patient Databases (LPDs) come directly from physicians' EMR. Participating physicians use CSD-provided software to record their daily patient interactions and data are transmitted regularly to the Cegedim coordinating center where they are cleaned and de-identified.

Data Sources: CSD's LPDs include data from 5.8 million active patients. Over 4,000 general practitioners (GPs) in six European countries (Belgium, France, Germany, Italy, Spain and United Kingdom) are part of the LPD panels.

Patient metrics in the LPDs include Demographics (Year of birth, gender, registration dates), Medical History (Event dates, diagnosis, symptoms, risk factors, co-morbidities, referrals), Prescription (Rx dates, indication, therapeutic class, molecule, brand, dosage, posology, duration), Clinical Data (Height, weight, BP, life habits) and laboratory data.

Exposures: A patient will be identified as newly exposed when he/she has at least one dapagliflozin prescription recorded in the study database(s).

Outcomes: Outcomes include but are not limited to:

- Patient demographics: age, sex, country,
- Baseline history of type 2 diabetes,
- Baseline history of moderate or severe renal impairment,
- Concomitant medications at baseline and during dapagliflozin use.

Follow-up: Follow-up will begin on the date a patient is first prescribed dapagliflozin, which will represent the beginning of follow-up (i.e., "index date"). Follow-up will continue until the end of study or discontinuation of dapagliflozin (i.e., the final day of the days' supply for the last prescription for dapagliflozin). Follow-up will only be used to determine combination use with loop diuretics or pioglitazone. The baseline period is defined as the 12 months in the database preceding the index date.

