1.2 Research Question

Research question 1: What are the baseline characteristics of the patients prescribed dapagliflozin in Europe?

Research question 2: What proportion of patients prescribed dapagliflozin have baseline moderate to severe renal impairment?

Research question 3: What proportion of patients prescribed dapagliflozin are 75 years of age or older at the time of the index prescription?

Research question 4: What proportion of patients prescribed dapagliflozin are also users of loop diuretics or pioglitazone during the baseline period and the available follow-up period?

Research Question 5: What proportion of patients prescribed dapagliflozin does not have a diagnosis of Type II Diabetes during the baseline period or on the index date?

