3.3.1 Content of the Cegedim LPDs

Data are entered during usual patient care and submitted daily to the Cegedim coordinating center, cleaned and de-identified and then made available in the LPDs for research no later than one month after submission. The following anonymized patient data collected from GPs' practice will be extracted from the databases:

- Demographics (Year of birth, gender, registration dates),
- Medical History (Event dates, diagnosis, symptoms, risk factors, co-morbidities, referrals,
- Treatments (indication, molecule/brand, dosage, posology, date and length of prescription),
- Clinical Data (Height, weight, BP, life habits),
- Clinical laboratory tests, X-ray and other investigations (not available in Germany).

The median follow-up duration of a patient in the data base is 27 months in Germany, 36 months in France, 44 months in Spain, 46 months in Belgium, 112 months in Italy and 117 months in UK.

Patient data collected by Cegedim in each country participating in the LPD varies to some extent to accommodate local needs. However, all countries collect data on medical co-morbidities and outcomes, prescriptions, demographics, and physician characteristics. Key metrics of the GPs' LPDs are provided for each country in Appendix 2 (2012 data).

In the LPDs, diagnoses of clinical events are recorded as diagnostic codes (*e.g.* ICD-9, READ). These codes from the different participating countries will be harmonized based on pre-specified algorithms developed prior to the analysis and listed in the statistical analytic plan. Table 3.3.1-1 summarizes the coding conventions for each of the databases.

Table 3.3.1-1: Data Coding Conventions in the Different Countries

	Belgium	France	UK	Italy	Germany	Spain
Drug code dictionary	Association Pharmacologique Belge	Claude Bernard	Multilex	Farmadati	Abdata	Vademecum
Therapy classification	European Pharmaceutical Marketing Research Association (EphMRA)		British National Formulary (BNF)	ATC	ATC	ATC
Disease classification	Cegedim prop thesaurus (mapped	-	Read Codes	ICD-9	ICD-10	CIAP mapped to ICD-9

ATC = Anatomic, Therapeutic, Chemical

ICD = International Classification of Disease

CIAP = International Classification of Primary Care

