3.4.1 Outcomes/Endpoint Variables

Table 3.4.1-1 includes the characteristics and definitions of how dapagliflozin users will be categorized and described.

Table 3.4.1-1: Categorization of Dapagliflozin Users

Characteristic	Definition
Patient Demographics, at initiation of dapagliflozin use:	
Age categories	< 45, 45-59, 60-74, >= 75
Sex	Male or Female
Country	Belgium, France, Germany, Italy, Spain, United Kingdom
Concomitant medications before, at initiation of and	Loop diuretics (ATC code C03Cx)
during dapagliflozin use 1	Pioglitazone (Actos, Glustin) (ATC code A10BG),
	Biguanides (ATC Code A10BA)
	Sulfonamide derivates (ATC code A10BB and A10BC)
	Dipeptidyl peptidase 4 inhibitors (DDP4) (ATC code A10BH)
	Glucagon-like peptide 1 (GLP-1, exenatide, liraglutide, ATC code A10BX),
	Alpha glucosidase inhibitors (ATC code A10BF).
	Insulin (ATC code A10A)
Concomitant co-morbidities, at initiation of dapagliflozin use:	
Baseline history of moderate renal impairment	CrCl or eGFR ² value between 30-60 within 12 months prior to the dapagliflozin dispensing
Baseline history of severe renal impairment	CrCl or eGFR value < 30 within 12 months prior to the dapagliflozin dispensing
Baseline history of renal failure	Diagnosis codes for end stage renal disease or dialysis (see Appendix 3)
Congestive heart failure	Diagnosis codes for congestive heart failure (see Appendix 3)
Hypertension	Diagnosis codes for hypertension (see Appendix 3)
Type 2 Diabetes Mellitus, at initiation of dapagliflozin use:	Diagnostic code for T2DM within 12 months prior to the dapagliflozin dispensing (see Appendix 3) OR
	Prescription for an antiglycemic medication within 12 months prior to the dapagliflozin dispensing

Table 3.4.1-1: Categorization of Dapagliflozin Users

Characteristic	Definition
Dapagliflozin Dose, at initiation of dapagliflozin	10 mg
use:	5 mg
Off-Label Use	Patients meeting one of the following criteria:
	 17 years old or younger on index date
	• 75 years of age or older on index date
	 No diagnostic codes for Type 2 Diabetes Mellitus, at or before the initiation of dapagliflozin use (see definition above)
	• Baseline history of moderate renal impairment (see definition above)
	• Baseline history of severe renal impairment (see definition above)
	• Baseline history of renal failure (see definition above)

^[1] Pioglitazone sales are suspended in France and Germany

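### Lack of type 2 diabetes is defined differently in RQ5, the synopsis and Table 3.4.1-1, and none of these names the indication recorded on the index prescription, so coding gaps and real off-indication use are poorly separated

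*Protocol*

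**What the plan says.** The protocol describes patients without T2DM in several places, and the rules differ.

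- **Synopsis, objectives:** the subgroup is "patients lacking a diagnostic code indicating type 2 diabetes". Section 2.1 speaks instead of patients not reported to have the disease.
- **Section 1.2, research question 5 (RQ5):** the proportion of patients who lack the disease, worded as "does not have a diagnosis of Type II Diabetes during the baseline period or on the index date".
- **Table 3.4.1-1, T2DM row:** a T2DM code in the 12 months before dapagliflozin, or an antiglycemic prescription in the same 12 months.
- **Table 3.4.1-1, Off-Label Use row:** "No diagnostic codes for Type 2 Diabetes Mellitus, at or before the initiation of dapagliflozin use", followed by a reference back to the definition higher in the table.

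On the indication field, the synopsis lists among the database metrics "Prescription (Rx dates, indication, therapeutic class, molecule, brand, dosage, posology, duration", and Section 3.3.1 lists among the data to be extracted "Treatments (indication, molecule/brand, dosage, posology, date and length of prescription". Section 5.1 says that "Recording of the indication of each prescribed treatment is mandatory in the Cegedim Software". The same sentence then warns that "the GP is free to enter any diagnosis and can for instance enter the reason of visit", and gives the example of an oral antidiabetic that carries flu as its indication.

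Section 4.1.1 commits the study to describing use inside and outside the labeled T2DM indication.

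**The concern.** The study asks whether dapagliflozin is prescribed outside its indication. It extracts the field in which the prescriber states what the drug was for, yet no classification rule gives that field a role. The rules that do exist disagree on whether an earlier antidiabetic prescription counts and on the time window.

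If off-indication use is rare, a small share of diabetics without a code can outnumber the real cases. The reported proportion would then reflect recording habits as much as prescribing. Under Section 4.3 the results go to the CHMP, and under Section 5.1 physicians cannot be asked for missing information, so the ambiguity cannot be resolved later by query.

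**Working it through.** The protocol states no figure for this point, so there is none to reproduce. The check has two parts.

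**1. The rules side by side**

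| Place | Code or diagnosis | Earlier antiglycemic prescription | Window | Index indication named |
|---|---|---|---|---|
| Synopsis | yes | no | not stated | no |
| RQ5 | yes | no | baseline or index date | no |
| T2DM row | yes | yes | 12 months before | no |
| Off-label row | yes | only through the cross-reference | at or before initiation | no |

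An uncoded diabetic with earlier antidiabetic treatment thus lacks T2DM under the literal RQ5 and synopsis wording, but has T2DM under the T2DM row. Under the code-or-prescription reading, the uncoded patients still misplaced are those with no antiglycemic recorded in the previous 12 months. The protocol itself points to two such groups: monotherapy starters (Section 1) and patients treated earlier by specialists, whose prescriptions the databases do not capture (Sections 5.1 and 5.2).

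**2. Size, with assumed rates**

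None of these inputs is in the documents:
- t = true off-indication share, 1%
- m = share of true diabetics without a qualifying code, 5%
- s = share of uncoded diabetics with an earlier antiglycemic prescription, 70% or 90%
- q = share of the remaining uncoded diabetics whose index indication correctly shows T2DM, 80%

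The formulas assume that neither the prescription nor the indication wrongly labels a real off-indication user as diabetic, and that q does not depend on s.

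- Code only: t + (1−t)m = 0.01 + 0.99 × 0.05 = 0.0595, about 6.0%. The real share is 10 of 59.5 per 1000, or 17%.
- Code or prescription: t + (1−t)m(1−s).
  - s = 70%: 0.01 + 0.0495 × 0.30 = 0.02485, about 2.5%. Real share 10/24.85 = 40%.
  - s = 90%: 0.01 + 0.0495 × 0.10 = 0.01495, about 1.5%. Real share 10/14.95 = 67%.
- Code, prescription or indication: t + (1−t)m(1−s)(1−q).
  - s = 70%: 0.01 + 0.01485 × 0.20 = 0.01297, about 1.3%. Real share 10/12.97 = 77%.
  - s = 90%: 0.01 + 0.00495 × 0.20 = 0.01099, about 1.1%. Real share 10/10.99 = 91%.

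With q = 60% the last two become 0.01 + 0.01485 × 0.40 = 1.6% and 0.01 + 0.00495 × 0.40 = 1.2%.

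**Sensitivity.** Keeping t = 1%, the code-only rule reads 0.01 + 0.99 × 0.02 = 3.0% for m = 2% and 0.01 + 0.99 × 0.10 = 10.9% for m = 10%. For t from 0.5% to 2% and m from 2% to 10%, the real share among flagged patients is 5-51% under code only. Under code or prescription, with s = 70% or 90%, it is 14-91%.

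**The case against.** The strongest reply has four parts.

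1. **The prescription limb already does much of the work.** The off-label row refers back to a definition that accepts earlier antidiabetic treatment, and outside monotherapy the label in Section 1 is for add-on use, so many initiators should have such a prescription. This stands. A reader might infer that every diabetic without a code is counted as off-label, or that the 3.0%, 6.0% and 10.9% figures apply to the off-label row. The table does not support that; those figures fit only the code-only wording of RQ5 and the synopsis.

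2. **The field may already count.** RQ5 admits a diagnosis on the index date, and Section 5.1 describes the indication as a diagnosis that the GP enters. Section 3.3.1 leaves the code algorithms to the SAP, which is not at hand. It therefore cannot be said that the plan shuts the field out. What stands is that the protocol does not say whether it counts, and that only RQ5 names the index date while the T2DM row looks only backwards.

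3. **The field is unreliable.** Section 5.1 says so in the sentence that calls it mandatory. This is a sound reason not to treat an entry such as flu as evidence of off-label use. The mechanism described there, a visit reason entered for every drug, mainly hides true T2DM indications. The documents give no error rate in either direction, however, and free entry could also produce false T2DM entries.

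4. **Completeness may vary.** The mandatory rule is stated for the Cegedim software, Appendix 1 also lists partner products, and Section 3.3.1 says that collected data differ by country. This stands, and is a reason to report by database.

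**Conclusion.** The point holds in a limited form. The T2DM rules in the synopsis, RQ5 and Table 3.4.1-1 do not agree, and none names an extracted field that bears directly on the question. As a result, coding gaps and real off-indication use are poorly separated. It would go too far to say that they cannot be told apart: earlier prescriptions separate them in part, and the indication would add to this without completing it.

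Under the assumed 1% and 5%, the choice between the protocol's own rules moves the result from about 6.0% to 2.5-1.5%. The indication takes off a further 1.2 points (2.485 − 1.297) to 0.4 points (1.495 − 1.099). The disagreement between definitions is thus the larger part and the unused field the smaller. All these sizes rest on assumed rates; no figure printed in the protocol is affected.

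**What to change.** - Use one T2DM definition, with one time window, for RQ5, the synopsis subgroup and the off-label row.
- Keep the code-or-prescription result as the primary figure. State that the indication on the index prescription does not count as an index-date diagnosis in it.
- Beside it, by database, show a version in which a T2DM indication on the index dapagliflozin prescription also confirms T2DM. Never use the field to prove off-label use.
- For patients without T2DM under the primary definition, tabulate the recorded indication: T2DM, type 1 diabetes, other specific condition, unrelated reason for visit, missing.

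The cost is wording in the protocol and SAP, a second version of one result and one table, from data already extracted. The downside is that some T2DM indications may be entered by habit and could hide off-label use, and that completeness may differ by software and country. Showing the result with and without the field, by database, makes both visible.

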5.2 Selection Bias

In order to more precisely describe the characteristics of European patients prescribed dapagliflozin (specifically baseline renal impairment), a minimum of 12 months (365 days) of medical history in the LPD is required prior to index date. Health care utilization patterns are best described when they include data from all potential prescribers of the drug. In this instance, the LPD data source does not capture prescriptions written in the specialist setting/hospitals; therefore, selection bias is possible if GPs prescribe dapagliflozin to a different patient population than a physician in a specialist setting. In the UK, the GP is a 'gatekeeper' of information for the patient and thus may be aware of and report health care visits or events taking place outside the GP setting. Thus, in the UK this selection bias may be less pronounced and UK THIN database can be used to estimate that selection bias in other databases.

5.3 Misclassification Bias

Misclassification bias can result if study subjects are not categorized correctly with regards to exposure or selected patient characteristics. We expect minimal misclassification with respect to exposure, since this will be determined from each database's prescribing records. However, actual adherence to dapagliflozin or other ADs cannot be confirmed. Further, misclassification as to whether the patient is a new initiator could exist (1) if providers supplied samples of dapagliflozin for varying duration to patients, at no cost, and with no record in the database and (2) if dapagliflozin was initiated by a specialist. This will vary by country and database, and could result in varying results across countries.

5.4 Generalizability

The study results will be generalizable to patients meeting the inclusion and exclusion criteria. However, by including data from the several countries in E.U., the study has the potential to maximize the populations to which these findings can be generalized.

6 STUDY CONDUCT

This study will be conducted in accordance with International Society for Pharmacoepidemiology (ISPE) Guidelines for Good Pharmacoepidemiology Practices (GPP) and applicable regulatory requirements.

6.1 Ethics Committee Review and Informed Consent

6.1.1 Ethics Committee Review

The investigator must ensure that the required approvals from Ethics Committees, Independent Review Committees, Regulatory Authorities, and/or other local governance bodies are obtained before study initiation at the site.

6.1.2 Informed Consent

This study does not require that informed consent is obtained from patients.

6.2 Responsibilities within the Study

The study shall be conducted as described in this approved protocol. All revisions to the protocol must be discussed with, and be prepared by BMS/AZ. The authors should not implement any deviation or change to the protocol without prior review.

6.3 Confidentiality of Study Data

The confidentiality of records that could identify subjects within the database must be protected, respecting the privacy and confidentiality rules in accordance with the applicable regulatory requirement(s). Documentation and archiving of the database may be implemented.

